5.2 Criteria for In-Study Decisions

In-study decisions will be made by the safety advisory committee (SAC), which will always comprise the Investigator, the Sponsor's representative medical monitor or the Sponsor's medically qualified designee who is familiar with the study protocol and Investigator's Brochure (IB), and a PK expert where appropriate.

5.2.1 Decision Points

The following in-study decisions will be made during this study:

- Dose level and prandial status selection for Regimen C.
- Whether to proceed with optional Period 4.
 - If Yes for Period 4, Dose level and prandial status selection for Regimen D

5.2.2 Criteria for Dose Level and Prandial Status Selection

Dose level and prandial status selection for Regimen C and Regimen D (if applicable) will only be made after a complete review of all data collected from the previous dose period(s). For dose level and prandial status selection to occur, data must be available from a minimum of 12 subjects who have completed the planned PK and safety assessments up to 48 hours after dosing. If data are not available for 12 subjects, the Investigator, Scientific Lead, and Sponsor will take a decision as to whether the data available are sufficient to support the dose level and prandial status selection decision. If data in fewer subjects are used in the decision process, additional subjects will not be dosed to increase the number of subjects in the completed regimen; however, additional subjects may be enrolled to achieve the target number of subjects for subsequent regimens.

Regimens C and D will only be administered in the fed state if the selected dose level has previously been administered in the fasted state.

The following data are required:

- AEs.
- Vital signs.
- ECGs.
- Safety laboratory tests.
- Plasma concentrations of delafloxacin.
- PK parameter estimates (Cmax, Tmax, AUC(0-last), AUC(0-inf) and Frel comparisons) up to 48 hours post-dose.

The dose(s) selected for Regimen C or Regimen D (if applicable) will only be selected from the design space of 300 mg to 600 mg.

The decisions on dose level and prandial status will be made by the SAC. The decision will be documented and signed by the Investigator as per Quotient Sciences' current standard operating procedure (SOP). Evidence of the decision will be retained in the ISF.

5.3 Study Sample Size

The study is exploratory, and no formal sample size calculation has been made. Based on experience from previous studies of a similar design, a sample size of 16 subjects and a minimum of 12 evaluable subjects is considered sufficient to meet the objectives of the study.

5.4 Randomisation (including Replacement Subjects)

Periods 1 and 2 are randomised; therefore, a randomisation schedule will be produced for these periods.

Instructions to dispense and dose will be produced prior to dosing using the randomisation schedule and will be retained in the ISF.

The original randomisation schedule and proof of quality control (QC) procedures will be held by the Data Sciences department at Quotient Sciences until the study is archived, at which time the randomisation materials will be retained in the ISF.

Using a computer-generated randomisation schedule, subject numbers will be allocated to one of two sequences in a 1:1 ratio (AB or BA [see [Table 1](#) for regimen details]). The allocation will be balanced, with 8 subjects receiving each sequence.

Subjects will be randomised immediately prior to dosing in Period 1.

Period 3 and optional Period 4 are non-randomised; therefore, a randomisation schedule will not be produced for these periods. Instructions to dispense and dose will be produced prior to dosing with IMP, which will dictate the order in which the treatments should be administered to each subject. The instructions to dispense and dose will be retained in the ISF.

5.5 Blinding Issues

This is an open-label study and therefore blinding is not required.

6 Populations and Analysis Sets

All safety and PK data will be presented by actual regimen received, regardless of mis-randomisation. For the statistical model, analysis set, disposition and demography tables, and listings, regimen sequence refers to the planned regimen sequence.

6.1 Safety Population and Safety Analysis Set

The safety population will include all subjects who have received any amount of IMP.

The safety analysis set will be defined on a per-regimen basis and will include all safety data from the subjects included in the safety population who have received that regimen.

The safety population will be confirmed by Quotient with approval from Melinta after database lock and will be summarised for the populations table and to determine the subjects to be included in the safety analysis set.

The safety analysis set will be confirmed by Quotient with approval from Melinta at the same time as the safety population and will be summarised for the analysis of demographic and baseline characteristics, and all safety data.

6.2 Pharmacokinetic Population and Pharmacokinetic Analysis Set(s)

The PK population will include all subjects who have received at least 1 dose of IMP and who satisfy the following criteria for at least 1 profile:

- No missing samples or invalid post-dose analytical results at critical time points, e.g., around Cmax
- No relevant protocol deviations that may impact the study objectives with respect to the PK endpoints
- No relevant AEs such as vomiting that suggest that the whole dose was not available for absorption for a particular subject

The PK analysis set will be defined on a per-regimen basis and will include all relevant data from the subjects included in the PK population who have received that regimen.

Individual subject profiles (i.e., regimens) will be excluded from the PK analysis set where deemed appropriate such as if the subject's data for the regimen affected did not meet the bullet point criteria above, or other study emergent point related to PK analysis or interpretation.

If required, a PK analysis subset(s) will also be documented by Quotient, with approval from Melinta, at the same time as the PK population and analysis set, if additional subjects are required to be excluded from the statistical analysis (for example to exclude subjects who have not received both the test and reference products).

The PK population will be used for the populations table. The PK analysis set and/or the PK analysis subset(s), if defined, will be used for the provision of PK summary tables and figures as well as the formal statistical analysis.

6.3 Taste/Palatability Population and Taste/Palatability Analysis Set(s)

The taste population will include all subjects who have completed at least one taste test, completed at least one question on the taste questionnaire, and do not have any relevant protocol deviations.

The taste analysis set will be defined on a per-regimen basis and will include all relevant data from participants included in the taste population who have received that regimen.

The taste population will be confirmed by Quotient with approval from Melinta after database lock and will be summarised for the populations table and to determine the subjects to be included in the taste analysis set.

The taste analysis set will be confirmed by Quotient with approval from Melinta at the same time as the taste population and will be summarised for the analysis of all taste data.

7 Subject Disposition, Demographics and Baseline Characteristics

No formal statistical testing will be performed on subject disposition or on demographic or baseline data. Summaries of subject disposition and analyses populations will be based on all enrolled subjects. Summaries of all other data described in this section will be based on the safety analysis set unless otherwise stated. All listings will be presented by all enrolled subjects.

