9.6 Interim PK Analysis

The details of the planned interim PK analysis are described in this section. However, as the analysis will be performed in real time, it may be necessary to change the planned analysis in response to the emerging data.

Summary tables and figures for the interim PK analysis will be presented in an Interim PK Summary Report after being exported from WinNonlin. The formatting of this output will differ slightly from the final PK output, which will be produced using SAS to include in the CSR.

The interim PK analysis will be performed on QC-checked delafloxacin concentration data in plasma using nominal sampling times and doses.

The following PK parameters will be calculated for the interim analysis:

delafloxacin Tablet (reference)

Tlag, Tmax, Cmax, AUC(0-24), AUC(0-last), AUC(0-inf), T1/2

delafloxacin Powder for Oral Suspension (test)

Tlag, Tmax, Cmax, AUC(0-24), AUC(0-last), AUC(0-inf), T1/2, Frel Cmax, Frel AUC(0-last), Frel AUC(0-inf)

10 Taste Assessments

Taste will be assessed for each of the delafloxacin Powder for Oral Suspension (i.e., test) regimens administered using a questionnaire (example provided in [Appendix 2](#)) immediately following test IMP administration.

Questions 1 and 2 within the questionnaire will ask subjects to rate the acceptability of 7 taste attributes (smell, sweetness, bitterness, flavour, mouth feel/texture, and aftertaste), as well as overall acceptability on a 9-point scale. For the purposes of continuous data summaries categories on the taste scale will be assigned numerical equivalents from 1-9 where 1 = 'Dislike extremely' to 9 = 'Like extremely'. No assumption will be made for summary statistics considered missing (i.e. recorded as "not detectable") but they will be included as a category.

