	450 MG TAB FASTED (N=X) n (%)	450 MG POS FASTED (N=X) n (%)	XXX MG POS <STATUS> (N=X) n (%)	XXX MG POS <STATUS> (N=X) n (%)
Subjects in safety analysis set	xx (xx.x)	xx (xx.x)	xx (xx.x)	xx (xx.x)
Reasons for exclusion from safety analysis set <All categories from source>	xx (xx.x)	xx (xx.x)	xx (xx.x)	xx (xx.x)

Note: Investigational Medicinal Product is delafloxacin, POS = powder for oral suspension, Regimen B, C and D with orange flavour
Regimen Key: A = 450 mg tablet (reference) fasted, B = 450 mg POS fasted, C = xxx mg POS <status>, D = xxx mg POS <status>
A subject may be excluded for more than one reason

PROGRAM PATH: X:\~\QSCXXXXXX\~\TFLS\PRODUCTION\TAB-XX DDMMYYYY HH:MM

Programming note: A similar table will be produced for the PK Analysis Set and Taste/palatability Analysis Set (and Subset[s], if required), i.e. Table [14.1.2.3] and Table [14.1.2.4]
Each analysis set/subset will be a subset of their respective population and percentages will be based on number of subjects in each population

Sponsor/Quotient Sciences Confidential

Melinta Therapeutics
Protocol: ML-DEL-101-3727-1

Page x of y

TABLE 14.1.3
Demographic and Baseline Characteristics
Summary Statistics: Safety Population

	n	Sequence		
		ABC<D> (N=X)	BAC<D> (N=X)	Overall (N=X)
Age (years)	n	xx	xx	xx
	Mean	xx.xx	xx.xx	xx.xx
	SD	xx.xx	xx.xx	xx.xx
	Median	xx.xx	xx.xx	xx.xx
	Min	xx.x	xx.x	xx.x
	Max	xx.x	xx.x	xx.x
Ethnicity n(%)	<All categories on source>	xx (xx.x)	xx (xx.x)	xx (xx.x)
Race n(%)	<All categories on source>	xx (xx.x)	xx (xx.x)	xx (xx.x)
Sex n(%)	Male	xx (xx.x)	xx (xx.x)	xx (xx.x)
	Female	xx (xx.x)	xx (xx.x)	xx (xx.x)
Height (cm)
Weight (kg)
BMI (kg/m^2)

Note: Investigational Medicinal Product is delafloxacin, POS = powder for oral suspension, Regimen B, C and D with orange flavour
Regimen Key: A = 450 mg tablet (reference) fasted, B = 450 mg POS fasted, C = xxx mg POS <status>, D = xxx mg POS <status>

PROGRAM PATH: X:\~\QSCXXXXXX\~\TFLS\PRODUCTION\TAB-XX DDMMYY YYYY HH:MM

Programming note: This table will continue for all categories of ethnicity and race
Height, Weight and BMI will be assessed using the same descriptive statistics as Age
If any values are missing, then a "missing" row will be included in the table, as applicable

Sponsor/Quotient Sciences Confidential

Melinta Therapeutics
Protocol: ML-DEL-101-3727-1

Page x of y

TABLE 14.1.4
Lifestyle Details: Smoking History and Alcohol Consumption
Summary Statistics: Safety Population

		Sequence		

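### SAP 6.3 applies the taste deviation criterion to the whole subject, so a deviation in one powder regimen also drops that subject's valid ratings for the other powder regimens from the taste summaries

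*SAP*

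**What the plan says.** SAP 6.3 sets three conditions for the taste population. The subject must have done at least one taste test, and must have "completed at least one question on the taste questionnaire, and do not have any relevant protocol deviations". The taste analysis set is then defined for each regimen and "will include all relevant data from participants included in the taste population who have received that regimen". That set is what the taste tables use: it is confirmed "at the same time as the taste population and will be summarised for the analysis of all taste data".

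The programming note to mock Table 14.1.2.2, which also governs the taste version (Table 14.1.2.4), states the hierarchy: "Each analysis set/subset will be a subset of their respective population and percentages will be based on number of subjects in each population".

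Taste is rated more than once per subject. SAP Section 10 says: "Taste will be assessed for each of the delafloxacin Powder for Oral Suspension (i.e., test) regimens administered using a questionnaire". Under SAP Table 1, the powder regimens are B, C and, if optional Period 4 is used, D.

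For PK, SAP 6.2 is built differently. The PK population takes subjects "who satisfy the following criteria for at least 1 profile", and the exclusion step works by regimen: "Individual subject profiles (i.e., regimens) will be excluded from the PK analysis set where deemed appropriate". The PK deviation criterion is also tied to the PK endpoints. In 6.3 the word relevant has no such anchor.

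**The concern.** One taste test is enough to meet the first two conditions in 6.3. The third has no matching qualifier, so a single relevant deviation at any point takes the subject out of the population. Because the per-regimen set is a subset of that population, the subject then contributes to no regimen.

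The foreseeable deviations belong to one period. Protocol 13.3 asks for the questionnaire to be started within 10 minutes of dosing, and for each test regimen to be rated independently of earlier questionnaires. A late start in Period 3 casts doubt on the Period 3 rating and on nothing else. What is at stake is the loss of sound ratings from a small descriptive data set, under a rule that differs from the SAP's own handling of the same situation for PK.

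**Working it through.** The plan gives no figure on this point, so there is nothing to reproduce. The logic can be followed from the text, and the size can be illustrated under stated assumptions.

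**Logic, for one subject given B, C and D with a relevant deviation in C only**

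1. SAP 6.3, population: the subject has a relevant deviation and is excluded.
2. SAP 6.3, analysis sets: these are drawn from the population, so the subject is absent from the sets for B, C and D. Three ratings leave Table 14.2.4, and two of them (B and D) are valid.
3. Under the structure of SAP 6.2: the subject qualifies through B or D, and only C is excluded. One rating leaves.

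Across 16 subjects and three powder regimens there are 16 × 3 = 48 planned ratings. One such deviation costs 3 of 48 under the written rule and 1 of 48 under a per-regimen rule.

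**Size**

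Inputs:
- n = 16 planned subjects (SAP 5.3).
- k = 2 powder regimens without Period 4, or 3 with it (SAP Table 1).
- p = probability that a given rating has a relevant deviation. The documents give none, so 2%, 5% and 10% are assumed, independent across regimens.

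Formulas, expected subjects kept per regimen:
- written rule: n(1 − p)^k
- per-regimen rule: n(1 − p)
- loss due to the rule: n(1 − p) − n(1 − p)^k

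| k | p | Per-regimen rule | Written rule | Extra loss per regimen | Valid ratings lost in total (k × extra loss) |
|---|---|---|---|---|---|
| 2 | 2% | 15.68 | 15.37 | 0.31 | 0.63 of 32 |
| 2 | 5% | 15.20 | 14.44 | 0.76 | 1.52 of 32 |
| 2 | 10% | 14.40 | 12.96 | 1.44 | 2.88 of 32 |
| 3 | 2% | 15.68 | 15.06 | 0.62 | 1.86 of 48 |
| 3 | 5% | 15.20 | 13.72 | 1.48 | 4.45 of 48 |
| 3 | 10% | 14.40 | 11.66 | 2.74 | 8.21 of 48 |

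Example, k = 3 and p = 5%: 16 × 0.95 = 15.20; 16 × 0.95³ = 13.72; difference 1.48.

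**The case against.** Four arguments stand on the other side.

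- **Low stakes.** Taste is the exploratory objective (SAP Section 4) and is only summarised descriptively (SAP 10.1). PK and safety have their own sets. This stands, and it sets the severity.
- **The ratings are not lost.** A reader might infer that they are deleted from the report. They are not: SAP 10.2 lists all taste data for all enrolled subjects, and SAP 7.2 and 7.3 provide for listing deviations and for reporting reasons for exclusion. The effect is confined to the population, the analysis set and Table 14.2.4.
- **Room for judgement.** Only relevant deviations count, the sets are confirmed with sponsor approval, and SAP 7.4 plans a table of exclusions from the taste analysis set by regimen. This suggests loose drafting rather than a deliberate choice, and a lenient reading is possible in practice. It does not cure the rule, because a per-regimen step cannot restore a subject already outside the population. Protocol 15.4 also expects the criteria to be defined before database lock, while the sets are determined after it.
- **Rates may be low.** Dosing is supervised with mouth checks (Protocol 11.3), so deviations affecting taste may be rare. At 2% the extra loss is under one subject per regimen. Three powder regimens arise only if optional Period 4 is used.

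A further stronger reading is that the most negative raters would leave the analysis, because someone who dislikes the suspension may not finish it. The documents do not support this. SAP 11.1 lists dosing deviations, but nothing says that an unfinished dose is a relevant deviation for taste. A per-regimen rule alone would drop that same negative rating. What the subject-level rule adds is the loss of the subject's other ratings, and nothing shows that those would be especially negative.

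**Conclusion.** The point holds as a minor defect in a stated rule. As written, SAP 6.3 omits valid ratings from the taste summaries whenever a relevant deviation is confined to one powder regimen, while SAP 6.2 treats the same case by regimen.

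The part that needs no assumption is that, with three powder regimens, one deviation removes three ratings, two of them valid. The expected size rests on assumed rates and on independence across regimens. It ranges from about 0.3 subjects per regimen (2%, two powder regimens) to 2.7 (10%, three).

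The gross loss should not be attributed to the rule. At 5% with three regimens it is 16 − 13.72 = 2.28 subjects, or 14%, but 0.8 of those would be lost under either rule. No primary or secondary result depends on this.

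**What to change.** Reword SAP 6.3 on the pattern of 6.2:

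- **Population:** subjects with at least one powder regimen for which at least one question was answered and no deviation affected the taste assessment of that regimen.
- **Analysis set:** exclude only the affected regimen and keep the subject's other ratings.

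A separate, conditional addition: if incomplete dosing because of taste would be classed as a relevant deviation, state that an answered questionnaire is kept in the taste summaries, since dropping it could favour positive ratings. This concerns the analysis set only.

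The cost is one or two sentences of SAP text, best settled before database lock. Study conduct, data collection and the PK and safety analyses do not change.

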7.1 Screening Failures

Data for subjects who have failed screening will be databased but will not be cleaned and therefore will not be included in the SDTM or ADaM datasets or any of the TFLs or the CSR.

7.2 Subject Disposition and Withdrawals

The number and percentage of subjects enrolled, dosed, completed, and discontinued will be presented by sequence and overall. If any subjects discontinued from the study early then the number of subjects for each reason for discontinuation will be presented by sequence and overall. However, if none of the subjects discontinued from the study early, then the reasons for discontinuation will not be populated in the summary table. A subject may be discontinued from the study early for 1 reason only.

Subject disposition and withdrawal data will be listed, including details of informed consent.

Protocol deviations and any violations of the inclusion/exclusion criteria will also be listed.

7.3 Analysis Populations

A summary table will be produced detailing the number and percentage of subjects in each population (i.e., safety, PK, and taste/palatability) by sequence and overall. The reasons for exclusion from each population will also be included in the summary table. However, if none of the subjects were excluded from a population, then the reasons for exclusion will not be populated in the summary table. A subject may be excluded from a population for more than 1 reason. The denominator for the percentage is the number of subjects enrolled in the respective sequence or overall.

Details of subjects included and excluded in the different analysis populations will be listed.

7.4 Analysis Sets and Subsets

A summary table will be produced detailing the number and percentage of subjects in each of the safety, PK and taste/palatability analysis sets and analysis subset/s (if applicable) for each regimen. Separate tables will be presented for safety, PK, and taste/palatability analysis sets and each table will be based on the relevant population the analysis set is derived from. If analysis subsets are defined, they will be included on the same table as the corresponding analysis set. The reasons for exclusion from each analysis set/subset will also be included in the summary. However, if none of the subjects were excluded from an analysis set/subset, then the reasons for exclusion will not be populated in the summary table. A subject may be excluded from an analysis set/subset for more than 1 reason. The denominator for the percentage is the number of subjects in each population.

Details of subjects included and excluded in the different analysis sets/subsets will be listed.

7.5 Demographic Characteristics and Lifestyle Details

Demographic data (year of birth, age, ethnicity, race, sex, height [cm], weight [kg], and body mass index [BMI; kg/m²]) will be recorded at screening.

Summary statistics (number of subjects with an observation [n], mean, standard deviation [SD], median, minimum, and maximum) will be presented for age, height, weight, and BMI at screening, by sequence and overall. The number and percentage of subjects will be presented by sequence and overall for ethnicity, race, and sex. The denominator for the percentage is all subjects in the safety analysis set for respective sequence or overall. If any values are missing, a “missing” row will be presented on the table.

Lifestyle details (i.e., smoking history [does the subject smoke, use e-cigarettes or use nicotine replacement products?] and alcohol consumption) will be summarised by sequence and overall, as categorical variables.

Demographic and lifestyle data will be listed (including weight at admission).

7.6 Medical/Surgical History

Medical/surgical history will be recorded for each subject at the screening visit and updated at admission. Medical histories will be coded using MedDRA v27.0 (or a more recent version), including Lower Level Term, Preferred Term (PT), High Level Term, High Level Group Term and System Organ Class (SOC). All medical/surgical history data will be listed including coded terms (SOC and PT).

